## B. Description of Population to be Enrolled:

We request a pilot group of up to 10 participants to establish the procedure and ensure the fMRI IBT training work wells at the UC Denver Brain Imaging Center in irritable youth. This study will target the total accrual of 100 youths, ages 13-17 years, drawn from a clinical sample, with at least mild, clinically significant irritability, typical intellectual functioning (IQ>80), absence of major medical problems, including head trauma. We anticipate 126 individuals may be enrolled allowing for 21% attrition and/or data loss. The total accrual target of 136 probands, who each require at least one caregiver to be involved, but we will not prevent another parent from participating. We will encourage one caregiver to fill out measures, as they are repeated measures. Based on prior experience, about 1.5 caregivers will be involved, yielding about 340 individuals on whom we will have collected information and 250 (100 probands plus 150 caregivers) who will be enrolled to generate sufficient data.

Additionally, we will recruit a small subsample from the same clinical population but with low irritable mood youth defined as parent-report ARI<3 and self-report ARI<2. Three volunteers will be uniformly assigned to each arm of the study at random.

Exclusionary diagnoses include current posttraumatic stress as well as lifetime bipolar I, II, cyclothymic, psychotic, and autism spectrum disorders. The rationale for these exclusions are to minimize confounds due to disorder-specific, face-emotion processing impairments or traumatic events. Exclusion criteria include clinical judgement of psychiatric instability and clinical high-risk status for danger to self or others. Exclusionary criteria include pregnancy. To operationalize some instability, any mental health treatment changes, new prescriptions of psychoactive medications, or substance use within 4 weeks of trial start will be considered exclusionary. Participants will be informed of these requirements during scheduling. A focus on adolescents maximizes comparison to prior work, ensures a more homogenous developmental level of face-emotion processing ability, and reduces age-related motion during fMRI or inattention to task.

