#### Randomization

Within 48 hours of Visit 1, Drs. [name] or [name] will determine if any exclusion criteria are met. This time allows Drs. [name] and [name] to consult each other or clarify information with the participants to achieve consensus for any unclear exclusionary diagnosis. If so, [name] will call the participants to thank for their participation, inform them of their exclusion, and cancel their second visit. Some exclusionary criteria are not stable, and it is likely the participants will be eligible during the study period. In that case, participants will still be

marked as a “Screen Failure,” in the consented, but not enrolled, category. However, they will be offered the opportunity to reschedule in the future. In this case, the participants will need to repeat visit 1.

During the pilot phase, eligible adolescents will not be randomized to a study arm, but will be invited to follow procedures for any arm. After pilot, eligible adolescents will be randomized for a 2 x 2 factorial, single blinded, randomized controlled trial, eligible adolescents will be assigned to one of four arms representing TRAINING (active or sham IBT) and SCANNING (in- or out-of-scanner IBT). First, scan ineligible patients will be assigned to out-of-scanner training. Second, randomization will use established minimization procedures (R packages randPack and/or randomizeR) to ensure the four arms are similar in terms of sex, age, socioeconomic status (SES), and IQ. The single blind is required so I may track adolescents with acceptable data. Acceptable behavioral data are at least 70% accuracy on extreme morphs (see [name] et al. for the development of this threshold) and, if applicable, scans of acceptable quality (see below). Allocation to any arm will end when the accrual goal of 25 adolescents with acceptable data have been reached for a total N=100. Since this is a small trial that is not intended to assess clinical efficacy, promoting power and ensuring balance across confounds outweigh the potential for allocation bias due to single-blinding or minimization procedures.

#### Training, Visit 2, Up to Day 7

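### Nothing separates the eligibility ruling from knowledge of past allocations under minimisation, so if the same person holds both, the next active/sham assignment can be guessed well above chance and selection can enter H1.2

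*Combined protocol and SAP*

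**What the plan says.** All of the following is in the Randomization section unless another place is named.

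- **Method.** Scan-ineligible adolescents first go to out-of-scanner training. Then "Second, randomization will use established minimization procedures" over four arms, "to ensure the four arms are similar in terms of sex, age, socioeconomic status (SES), and IQ". The software is left as "R packages randPack and/or randomizeR". No assignment probability, tie rule, factor categories, weights, operator or concealment step is given. The superscript on the method points to a study of hostile intent attributions in the reference list, so the citation does not fill the gap.
- **Blinding.** "The single blind is required so I may track adolescents with acceptable data". Each arm closes at 25 adolescents with acceptable data.
- **Eligibility.** Within 48 hours of Visit 1, and before allocation, one of two doctors "will determine if any exclusion criteria are met". Under Description of Population to be Enrolled, "Exclusion criteria include clinical judgement of psychiatric instability".
- **Deferral.** Adolescents who fail on a criterion that may change are recorded as screen failures, but "they will be offered the opportunity to reschedule in the future", with Visit 1 repeated.
- **Acknowledgement.** The plan judges that power and balance "outweigh the potential for allocation bias due to single-blinding or minimization procedures", because the trial is small and not aimed at clinical efficacy. No mitigation is described.

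**The concern.** Minimisation makes the next assignment depend on the running totals and on the new adolescent's factor levels. Someone who knows past allocations can therefore often tell which training arm is favoured. If that person also decides whether a borderline adolescent enters now, later or not at all, the arms can come to differ on things that are not minimised, such as motivation, cooperation or expected response to training. Balance on sex, age, SES and IQ does not prevent this, and adjustment for measured covariates cannot fully remove it.

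What is at stake is H1.2, the randomised active-versus-sham test of whether training moves hostile interpretation bias. On the trained-face balance point, which is measured before and after training, selection has to act mainly through expected change. The NimStim face task (Visit 2) and the Intent Attributions Questionnaire (online follow-up) are collected only after training. They have no baseline of their own, so an imbalance between arms passes straight into the comparison.

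This is separate from the closing of arms near the end of accrual. It operates from the early entries onward.

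**Working it through.** **Plan's own figure.** The documents give no figure for predictability and no numerical power for H1.2, so there is nothing to reproduce on this point. The enrolment input is consistent to within one person: 100/(1 - 0.21) = 126.6, against 126 stated.

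**Inputs from the documents.** Four arms; four factors; 126 enrolled; 21% loss; arm closure at 25 acceptable; 50 active and 50 sham analysed.

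**Assumptions.** Sex in 2 levels; age, SES and IQ in 2 or 3 levels (age also tried in 5); 0%, 15% or 20% scan-ineligible; imbalance measured as the sum of ranges of the marginal counts. The guesser knows all past allocations, the adolescent's factor levels, and the cut-points and weights.

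**Step 1: predictability.** Two set-ups were simulated, with 300 trials per setting. Set-up A has 126 entries and no arm closure. Set-up B has 21% loss and closure at 25.

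| Probability for favoured arm | Correct guess, A | Correct guess, B | Certain assignments | Mean imbalance per factor level, A (persons) |
|---|---|---|---|---|
| 1.0 (deterministic) | 90-91% | 91% | 79-81% | 0.9-1.0 |
| 0.9 | not run | 85-86% | 3% (B, late) | not run |
| 0.8 | 78-79% | 79-80% | none (A); 3-4% (B, late) | 1.4-1.7 |
| 0.7 | 71-73% | 74% | 4% (B, late) | 1.9-2.2 |
| Simple randomisation | 50% | 54-55% | 6-7% (B, late) | 5.3-6.2 |

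In set-up B over the first 80 entries, the deterministic rule is still guessed at about 90%, the 0.8 coin at about 78%, and simple randomisation at 50%. The excess over 50% for simple randomisation in the full run comes from arm closure. A person who cannot see the allocations is at about 50% under any of these rules.

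**Step 2: what a guess could do (illustrative).** Let G be the correct-guess rate. Suppose selection shifts expected outcome by +d SD when active is guessed and by -d SD when sham is guessed. Then:

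- bias = 2 × d × (2G - 1)
- standard error of the difference at 50 per arm = sqrt(2/50) = 0.2 SD, so noncentrality = 5 × bias
- two-sided 5% error = P(Z > 1.96 - 5 × bias) + P(Z < -1.96 - 5 × bias)

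| d (SD) | G = 0.907: bias, error | G = 0.78: bias, error | G = 0.50 |
|---|---|---|---|
| 0.05 | 0.08 SD, 6.9% | 0.06 SD, 5.9% | 0, 5% |
| 0.10 | 0.16 SD, 12.9% | 0.11 SD, 8.7% | 0, 5% |
| 0.20 | 0.33 SD, 37% | 0.22 SD, 20% | 0, 5% |

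Example: 2 × 0.10 × (2 × 0.907 - 1) = 0.163; 5 × 0.163 = 0.81; error 12.9%.

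**Step 3: the same question through deferral.** Let 10%, 20% or 30% of adolescents with an unfavourable latent trait be turned away when the next arm is guessed, with no true effect. Under the deterministic rule the active-sham shift is 0.07, 0.14 or 0.23 SD and the error about 8.5%, 13% or 20%. With the 0.8 coin it is 0.04, 0.12 or 0.15 SD and 6%, 10% or 12%. With simple randomisation it is at most 0.02 SD and 3.5-4.8%. These deferral rates are assumed; the documents give none.

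**The case against.** The best defence has four parts.

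**Silence is not determinism.** A reader might infer that roughly nine in ten assignments are foreseeable under this plan. The documents do not support that: they call the method randomisation, leave the probability open, and list no SES measure among the Visit 1 forms, so full knowledge of the factors is also assumed. This stands, and 91% is an upper figure. It does not rescue the arrangement, because a 0.8 coin still leaves 78-79% for someone who knows the past allocations and factor details.

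**There are partial safeguards.** The two doctors may consult to reach consensus on unclear diagnoses. Diagnoses come from a semi-structured interview. Part of the instability criterion is made operational by a 4-week window on treatment changes, new psychoactive prescriptions and substance use. A deferred adolescent must repeat a visit of 3 to 3.5 hours. The analysis plan also checks anxiety, depression and pubertal development for imbalance. These narrow the room for selection. They do not close it: a clinical judgement remains, and consultation can carry allocation knowledge from one doctor to the other.

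**The primary measure is hard to steer.** The balance point comes from keypresses, is first measured at Visit 2 after the ruling, and is modelled before and after training. Stable differences in level do not create a condition-by-time effect. This stands for the trained faces, but not for the measures taken only after training.

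**The risk was accepted openly.** It was, and the disclosure is to the plan's credit. But the stated reason is power and balance, and separating the roles costs neither. That the trial does not assess clinical efficacy does not cover H1.2, which is a randomised comparison.

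**Conclusion.** The point holds as a conditional one, and the change is worth making because it is cheap. The documents establish minimisation without a stated probability, an unblinded author, an eligibility ruling that is partly judgement, re-entry after deferral, and no separation between the ruling and past allocations. If the person ruling knows those allocations, guesses run at about 78-79% with a 0.8 coin and up to about 91% if the rule is deterministic and all factor details are known.

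Three stronger readings should be resisted.

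- That the unblinded author is one of the two eligibility doctors is likely but cannot be shown, since names are removed.
- That H1.2 has a type I error of 13%, or any other particular value, is not supported. The 7% to 37% range rests on assumed shifts of 0.05 to 0.2 SD and the 91% guess rate, and the plan expects a large training effect in any case.
- That a go/no-go decision hangs on H1.2 is not what section G says. The term there describes the later efficacy trial, and no decision rule is tied to this hypothesis.

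Nothing here suggests misconduct.

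**What to change.** Amend the Randomization section as follows.

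1. **Separate the roles (the essential step).** The eligibility ruling and any deferral, with its reason, are made and locked in REDCap before the allocation program is run, by a doctor without access to past allocations. Consultation with an unblinded colleague is limited to the facts of the case.
2. **Move the totals.** The data coordinator already mentioned in section C runs the program, holds the running totals and supplies arm-level counts of acceptable data for arm closure. Those counts should not reach the doctor who rules.
3. **Add a random element (secondary).** For example, give the favoured arm probability 0.8, and state the tie rule, factor categories, weights and package. Alone this is not enough, as the 78-79% shows.
4. **Keep the sentence on allocation bias,** say how the bias is mitigated, and report deferrals and re-entries by arm, counting those later allocated under the arm they received.

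**Cost.** A short amendment and one setting in the allocation code. There is some restriction on which doctor may rule and on consultation; the documents do not say that either doctor is currently kept from the allocations, so this has to be arranged. With the 0.8 coin, mean active-sham imbalance per factor level rises from about 1.0 to about 1.4-1.7 persons, still far below the 5 to 6 under simple randomisation. The telephone screen comes before the locked ruling, so some scope for selection remains if an unblinded person conducts it.

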## B. Study Design and Research Methods

Participants will complete two study visits and one online assessment, with procedures listed in this table and described below.

### Assessment, Visit 1, Day 1

This visit will occur at the Pediatric Mental Health Institute (PMHI) outpatient clinic in a private laboratory room (see COMIRB Application, Section Q, for facilities description).

Adolescents and their parent will begin with a session to obtain informed consent and assent with study personnel (see COMIRB Application, Section L, for procedure). Clinical assessment will begin with the parent and adolescent will each complete their respective versions of the Affective Reactivity Index (ARI) to

Clinical Assessment	Training	Post training Assessment
Day 1	Up to Day 7	1 week ± 3 days after training
Clinic	Clinic	Online
Consent	IBT	ARI
ARI		Scales
WASI		
KSADS		
C-SSR		
Scales		

measure level of irritability. Adolescents with mild clinical irritability will be invited to continue (parent-report ARI  $\geq$  3 or self-report ARI  $\geq$  2; based on sensitivity analyses in Kircanski et al.).

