#### **F. Data Analysis Plan:**

Development of Computational Models. The application of computational models of learning to behavior and neural response is integral to both the training and scientific aims of this proposal. We will apply well-established models of human reinforcement learning (variants of Rescorla-Wagner and Pierce-Hall that incorporate stimulus generalization) and assess their fit to IBT data. Goodness of fit will be assessed with expectation-maximization and maximum-likelihood algorithms. Models will also be tested in secondary analyses of IBT data of youths with DMDD from [name] lab. The parameters for the model will be (a) parameters determining initial value, i.e. probability of angry, for each stimulus, (b) learning rate, (c) a parameter determining degree of generalization among stimuli, (d) reliability of judgments (inverse choice temperature). Simulation of the model under parameters estimated from the data will yield predictions for the trialwise likelihood that each face is considered angry and of the trialwise prediction error. (Note: these last two variables could be used as predictors in the fMRI analysis.) For transparency, analytic code (not any data) for all models will be posted to online software development repositories.

Hypothesis Testing. To maintain rigor, all analyses will involve omnibus models with appropriate diagnostics for model fit and influential data. Minimization procedures should ensure balance on the environmental and biological factors (sex, age, SES, and IQ) that may influence hypothesized associations. Additional potential factors are anxiety, depression, pubertal development, and in- or out-of-scanner training. The effects of all of these factors on independent variables will be assessed. If an imbalance across training groups occurs in any of these factors or a significant association is detected between these factors and an independent variable, it will be entered into the omnibus model as a covariate.

Hypothesis 1.1: Baseline hostile interpretation bias is associated with baseline irritability. Linear regression with pre-training balance point (interpretation bias) as a dependent variable and pre-training ARI (irritability) as an independent variable.

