Hypothesis 1.2: Active but not sham, IBT will reduce hostile interpretation bias. Mixed-effects linear regression with balance point (interpretation bias) as a dependent variable and training condition (active vs. sham), and time of interpretation bias assessment (pre- or post-training) as independent variables of interest and person as a grouping variable and random effect. Similar models will test for group differences in active or sham IBT on other measures of hostile interpretation bias after training.

Hypothesis 2.1: The rate of learning new associations to ambiguous faces training will be associated with baseline irritability. For those in the active condition, linear regression will test the association between pre-training ARI (irritability) and learning rate to reversal feedback of baseline angry judgments to the two ambiguous morphs.

Hypotheses 2.2 and 2.3: Active, but not sham, IBT will evoke greater neural response in threat-learning systems. For each person, learning will be modeled with regressors coding the “value” or trialwise likelihood that a participant considers the morph to be angry. The amplitude of BOLD %signal change (activity) or amygdala covariance (generalized psychophysiological interaction; connectivity) related to these regressors represents neural response to value. Critically, these regressors represent learning itself where value is changing towards benign judgments in the active training condition to two ambiguous morphs. These will be carried forward to the second level mixed-effects linear models of the effects of morph by pre-training ARI by training condition. A voxel-wise threshold of  $p < .001$ , whole-brain, cluster corrected to  $p < .05$  via permutation testing or Monte Carlo simulation as appropriate, will be used to identify significant associations. A three-way interaction of change in value by morph by training condition will indicate neural areas where learning is influenced by irritability in active but not sham training of reversals of ambiguous morphs. In addition, our *a priori* identification of the likely role of the amygdala, OFC, and ACC justifies follow-up region-of-interest analyses of mean activity or connectivity extracted from these areas with the same omnibus mixed-effects model.

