Exploratory Hypothesis 3.1: Change in irritability after training is associated with change in hostile interpretation bias. We will investigate this relationship with mixed-effects linear models with ARI (irritability), balance-point (interpretation bias), and time of assessment (pre- or post-training) as within-person variables.

Exploratory Hypothesis 3.2: Change in irritability after training is associated with magnitude of neural threat-learning system response. We will investigate this relationship with mixed-effects linear models with ARI (irritability), mean value-associated connectivity or activity in the amygdala, OFC, and ACC, and time of assessment (pre- or post-training) as within-person variables.

As requested by NIMH scientific review, I will conduct two additional, secondary analyses: 1) a mediation analysis of active IBT on change in irritability and 2) a multivariate analysis of the shared and unique effects of irritability, anxiety, and depression on hostile interpretation bias.

Power analysis. For Aim 1, a sample size of 100 achieves 80% power to detect an effect size of the expected association of at least  $r = .25$  between baseline hostile interpretation bias and baseline irritability using Pearson correlation at a one-tailed alpha of .05. Thus, the proposed study will have sufficient power to detect small to medium sized interaction effects. The study is overpowered for detecting expected effects of IBT on hostile interpretation bias which should be large. For Aim 2, a sample size of 100 likewise achieves more than 80% power to detect the expected large association between baseline irritability and learning. For imaging, using a medium effect size of a term in a general linear model ( $R^2 = .15$ ), the required sample for 80% power is 50 individuals ( $p = .05$ ). Our previous study that examined IBT-related changes to face-emotions was medium to large in the orbitofrontal cortex. Thus, the proposed study will have sufficient power to detect small to medium sized interaction effects. Aim 3 is exploratory; this study may estimate effect sizes for future research.

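### Baseline ARI is known before allocation but is not a minimization factor, leaving the post-training-only bias contrasts and the mediation analysis open to chance imbalance (cheap improvement, low to moderate priority)

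*Combined protocol and SAP*

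**What the plan says.** The Randomization section describes a 2 x 2 design (active or sham, in or out of scanner) with 25 analysable adolescents per arm. Minimization is used "to ensure the four arms are similar in terms of sex, age, socioeconomic status (SES), and IQ". The Data Analysis Plan, under Hypothesis Testing, repeats the same four: "Minimization procedures should ensure balance on the environmental and biological factors (sex, age, SES, and IQ) that may influence hypothesized associations". It then adds anxiety, depression, pubertal development and scanner setting as further candidates. An imbalance between training groups on any listed factor triggers its entry as a covariate. ARI is on neither list.

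ARI is available in time. Under Assessment, Visit 1, "Clinical assessment will begin with the parent and adolescent will each complete their respective versions of the Affective Reactivity Index (ARI) to" measure irritability, and the score decides entry: "Adolescents with mild clinical irritability will be invited to continue (parent-report ARI" at or above 3, or self-report at or above 2). Allocation comes after the eligibility review: "Within 48 hours of Visit 1, Drs. [name] or [name] will determine if any exclusion criteria are met".

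ARI then appears in three kinds of analysis that involve training or its effects:
- Hypotheses 2.2 and 2.3 use "second level mixed-effects linear models of the effects of morph by pre-training ARI by training condition".
- Exploratory Hypothesis 3.1 uses "mixed-effects linear models with ARI (irritability), balance-point (interpretation bias), and time of assessment (pre- or post-training) as within-person variables", and 3.2 has the same structure with neural response.
- A secondary analysis is "a mediation analysis of active IBT on change in irritability".

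Other measures of hostile interpretation bias are compared between active and sham after training, with models like that for Hypothesis 1.2. That model names training condition and time, not ARI.

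**The concern.** The plan's own reason for balancing a factor is that it may influence the hypothesized associations. Hypothesis 1.1 states that ARI is related to hostile interpretation bias, with an expected r of .25, so ARI meets that test. The same section justifies minimization and the single blind by the value of balance and power in a small trial.

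A chance ARI difference between active and sham matters where a comparison has neither its own baseline nor an ARI term. The NimStim assessment is described only after training, and the Intent Attributions Questionnaire can be given only once. They carry the question of whether training generalizes, which the Background summary ties to Hypothesis 1.2. The mediation analysis is exposed for another reason: if ARI change is compared between arms without adjustment, the arm that starts higher tends to fall more through regression to the mean.

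**Working it through.** **1. The plan's own figures.** Aim 1 (N = 100, r = .25, one-tailed .05): power = Φ(atanh(.25) × √97 − 1.645) = 80.8%, against 80% stated. Imaging (R² = .15, so r = .387, two-sided .05): N = ((1.960 + 0.842)/atanh(.387))² + 3 = 50.0, against 50 stated. Both reproduce. Neither formula uses ARI balance, so the stated sample sizes are unaffected.

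**2. Which analyses depend on active-sham ARI balance.**

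| Analysis | Dependence |
|---|---|
| H1.1 | None: arms pooled, before training |
| H1.2, balance point | Little: the outcome has its own pre-training value in the model |
| H1.2, other bias measures after training | Yes: no baseline described, no ARI term stated |
| H2.1 | None: active condition only |
| H2.2, H2.3 | Precision only: ARI is in the model |
| H3.1, H3.2 | No between-arm contrast stated |
| Mediation of ARI change | Yes: no baseline adjustment stated |

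**3. Size of a chance imbalance.** If ARI is unrelated to the four factors, the standardized difference in mean ARI has SD √(2/n), and P(gap > d) = 2[1 − Φ(d/SD)].

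| Comparison | SD | > 0.3 SD | > 0.4 SD | > 0.5 SD |
|---|---|---|---|---|
| 25 v 25 (scanned) | 0.28 | 29% | 16% | 8% |
| 50 v 50 (all) | 0.20 | 13% | 5% | 1% |

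**4. Effect of adding ARI.** Four-arm range-based minimization was simulated with a biased coin of .8, continuous factors in tertiles, ARI independent of the other factors, and 1,200 to 1,500 runs per setting.

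| Gap > 0.3 SD | As planned | ARI added |
|---|---|---|
| In-scanner, 100 allocated, no loss | about 29-31% | about 7-9% |
| In-scanner, 126 allocated, 21% random loss | about 25-28% | about 13% |
| All active v all sham, no loss | about 14% | about 2% |

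The SD of the arm difference in IQ moves from 0.167 to 0.177, so the existing factors lose almost nothing.

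**5. What an imbalance does.**
- *H2.2, H2.3.* For a two-way ARI by training term with partial R² .15 at N = 50, average power rises from 78.4% to 80.6% with idealized balancing on ARI, and from 79.5% to 81.2% with simulated minimization.
- *Post-training-only measures.* Shift = r × gap. Taking the plan's r = .25 to hold for these measures too: .25 × 0.3 = 0.075 SD and .25 × 0.5 = 0.125 SD. All participants contribute, so the 50 v 50 probabilities apply.
- *Unadjusted ARI change.* Shift = gap × (1 − ρ), where ρ is the pre-post correlation. The documents give no ρ; for an assumed .8 to .5, a 0.5 SD gap gives 0.10 to 0.25 SD, and a 0.3 SD gap gives 0.06 to 0.15 SD.

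**The case against.** Chance imbalance of this size is ordinary under randomization and already reflected in the standard errors. The trial is not meant to assess clinical efficacy, Aim 3 is exploratory, and covariate adjustment would deal with the exposed comparisons without touching allocation. ARI's absence from the imbalance list is partly by construction, since that list concerns influences on the independent variables and ARI is itself the independent variable in several hypotheses. All of this stands, and it limits the priority. It does not remove the gap, because no such adjustment is stated for the exposed comparisons.

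Three stronger readings are tempting, and the documents do not support them:
- A reader might infer that nothing in the plan controls an ARI difference. Pre-training ARI is a term in the second-level imaging model, and the region-of-interest follow-up uses the same model. Imbalance there costs precision and causes no bias.
- A reader might take the 25-31% figure as the damage to the ARI by condition contrast. The precision of that contrast depends on ARI spread within arms, not on the gap between arm means. In simulation the gap and the variance of that slope were essentially uncorrelated (about 0.01).
- A reader might infer that Hypotheses 3.1 and 3.2 are distorted by unequal regression to the mean. Neither states a between-arm contrast.

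The small low-irritability group, three per arm, is a separate addition and does not balance ARI among the main 100.

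**Conclusion.** The omission is real and its consequences are modest. No hypothesis test is invalidated and no stated sample size changes. The imaging hypotheses lose about 2 power points on average. The exposed comparisons are the active-sham contrasts on the NimStim set and the Intent Attributions Questionnaire, and the mediation analysis. A 0.3 to 0.5 SD gap would move the first group by about 0.08 to 0.13 SD. A 0.5 SD gap would move an unadjusted ARI-change contrast by 0.10 to 0.25 SD. These are shifts in a particular unlucky allocation, not bias on average over allocations.

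The figures assume that ARI is independent of the four factors (correlation would lower the planned risk somewhat), that data loss is random, and that r = .25 carries over to the other bias measures. The simulations do not model the prior assignment of scan-ineligible adolescents to the out-of-scanner arms. This is a cheap improvement of low to moderate priority.

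**What to change.** 1. In Randomization, add baseline ARI as a fifth minimization factor. Name one informant, parent or self, because either can qualify a participant. Fix the categories in advance; the documents give no ARI distribution from which to set tertiles, so the source of the cut-points must be stated.
2. In the Data Analysis Plan, pre-specify baseline ARI as a covariate in the active-sham comparisons of the post-training-only bias measures and in the mediation analysis. This also covers imbalance that arises from data loss, which minimization cannot prevent. Add ARI to the list of factors checked for imbalance in these comparisons.

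The ARI data are already collected before allocation, so there is no added burden on participants and no change in sample size. The cost is a small change to the allocation program, a decision on informant and cut-points, and very slightly looser balance on sex, age, SES and IQ. The allocation change helps only participants not yet allocated; the covariate can be specified at any time before the data are examined by arm.
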